6.0 Treatment Plan

6.1 Treatment Regimen Overview Consent and Screening

Upon signing consent, patients will begin the screening phase. The screening period begins the day the patient signs consent and can take place over a 28 day period leading up to dosing on day 1 (D1). During the screening period patients will be assessed to determine if they meet eligibility for this study per the inclusion and exclusion criteria as outlined in sections 4.1 and 4.2. Once the patient is deemed eligible they will be stratified into two arms based on the post-HMA failure model (Appendix V).

Stratification

Prior to beginning treatment, all eligible patients will be stratified into low vs. high risk based on the post-HMA failure model (Appendix V)⁴. Seven patients will be enrolled into the low risk arm and seven patients will be enrolled into the high risk arm. Once 14 patients, across both arms, have been enrolled and evaluated for a response (D35 +/- 10 days bone marrow), an interim analysis will be conducted to determine benefit in

each arm. The arm with the greatest response will then enroll an additional 11 patients, for a total of 18 patients in that arm. Overall, this study will enroll 25 patients.

Induction

The induction phase is defined as the time between the first day (D1) of study drug to day 35 and/or count recovery. During the induction phase of the study, all patients will be treated with the FDA approved standard dose of CPX-351 at 44mg/m² (daunorubicin 44 mg/m² and cytarabine 100 mg/m²) on days 1, 3, and 5. Study drug will be administered per the study calendar (section 11.2) unless patient exhibits any EOT criteria. Premedication with anti-emetics is recommended prior to treatment with CPX-351. No re-induction will be allowed and no day 14 bone marrow biopsy is required. A bone marrow biopsy and aspirate will be obtained on day 35 +/-10 days to confirm response. If no evidence of blasts > 5%, G-CSF will be allowed to improve counts at the discretion of the treating physician. Following the bone marrow, patients who meet the response criteria per section 12.0 can then continue onto the consolidation phase of this study.

Consolidation

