14.0 STATISTICAL CONSIDERATIONS

In determining the sample size for the patient cohort, Minimax Simon's two-stage design (Simon, 1989) will be used. The null hypothesis that the true response rate is 0.1 will be tested against a one sided alternative. In the first stage, 7 patients will be accrued in each arm. If there are two or less responses in these 7 patients, the arm will be stopped. Interim analysis will be conducted to determine the benefit of applying the drug in each arm. In the winning arm, 11 additional patients will be accrued for a total of 18. The null hypothesis will be rejected if 4 or more responses are observed in 18 patients. This design yields a type I error rate of 0.1 and power of 0.8 when the true response rate is 0.3.

Descriptive statistical analysis will be calculated, including histograms or box-plots, proportions, range, means and standard deviations. Fisher's exact test and Wilcoxon rank test will be used in univariate analyses of categorical and continuous variables, respectively. Overall response (CR + CRI +) rate and its 95% CI. Given there is no adjustment for multiple comparisons, need to note the p-values from the univariate analyses will be nominal and not used to infer significance.

Toxicity Monitoring Rules

The following toxicity monitoring plan will terminate the trial early given evidence for excessive rates of toxicity with CPX-351 based on the method of Thall et al.¹⁴ Early termination will be applied to evaluate patients experiencing toxicity defined as any grade ≥ 3 non-hematologic AE that is determined to be at least possibly related to CPX-351. A total of 25 patients will be enrolled. The monitoring rules target a toxicity rate of 20% and assume a non-informative Beta (0.2, 0.8) prior distribution. The trial will stop early for toxicity if $\text{Pr}(\text{Toxicity Rate} > 0.20 | \text{data}) > 0.85$, i.e. stop early if the evidence for excessive toxicity (higher than 20%) for the target population given observed data is sufficiently high (probability > 0.85). Monitoring will be carried out

from the 3rd patient. Table 5 summarizes the resultant stopping boundaries and Table 6 summarizes the trial's operating characteristics.

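### When both arms have two or fewer responses in 7, Section 6.1 calls for expansion to 25 patients while Section 14.0 stops both arms, and neither section has a tie rule

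*Combined protocol and SAP*

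**What the plan says.** Section 6.1 (Stratification) enrolls seven low-risk and seven high-risk patients and holds an interim analysis once all 14 have been evaluated for response. It then directs: "The arm with the greatest response will then enroll an additional 11 patients, for a total of 18 patients in that arm". The paragraph ends: "Overall, this study will enroll 25 patients". It names no response count below which expansion is withheld.

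Section 14.0 specifies that "Minimax Simon's two-stage design (Simon, 1989) will be used" and that "The null hypothesis that the true response rate is 0.1 will be tested against a one sided alternative". Its stage-1 rule is: "If there are two or less responses in these 7 patients, the arm will be stopped". It continues: "In the winning arm, 11 additional patients will be accrued for a total of 18". The final rule is: "The null hypothesis will be rejected if 4 or more responses are observed in 18 patients". The stated operating characteristics are a type I error of 0.1 and power of 0.8 at a true rate of 0.3.

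Nothing in the document ranks one section above the other. Neither section covers equal response counts, and Section 14.0 does not say what follows if both arms stop.

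**The concern.** There are three types of interim outcome.

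- **At least one arm has 3 or more responses and the counts differ.** The sections agree: the better arm expands.
- **Both arms have 2 or fewer.** Section 6.1 continues to 25 patients and Section 14.0 ends enrollment at 14. Following Section 6.1 would treat 11 more patients in an arm that the statistical section has stopped.
- **The counts are equal.** There is no single best arm. The arm that expands is the population in which the primary hypothesis is tested, so an unplanned tie-break would choose that population after the responses are known.

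**Working it through.** **Inputs.** From Section 14.0: 7 patients per arm at stage 1, stop at 2 or fewer, 11 more in one arm, reject at 4 or more of 18, null rate 0.1, alternative 0.3. From Section 6.1: the arm with more responses expands, total 7 + 18 = 25. Assumption: responses in the two arms are independent.

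**Step 1. The plan's own figures.** For one arm with stage-1 limit r, P(reject) = Σ over x > r of P(Bin(7,p) = x) × P(Bin(11,p) ≥ 4 − x).

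| Stage-1 limit | Type I error (p = 0.1) | Power (p = 0.3) |
|---|---|---|
| 2 of 7 (as written) | 0.0185 | 0.348 |
| 1 of 7 | 0.056 | 0.630 |
| 0 of 7 | 0.0893 | 0.8000 |
| no interim stop | 0.0982 | 0.835 |

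The limit as written does not give the stated 0.1 and 0.8. A limit of 0 of 7 does, taking 0.1 as a ceiling, and an exact search returns 0/7 then 3/18 as the minimax design. Both limits are therefore carried forward.

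**Step 2. Both arms at or below the limit.**

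- P(Bin(7, 0.1) ≤ 2) = 0.4783 + 0.3720 + 0.1240 = 0.9743
- P(Bin(7, 0.3) ≤ 2) = 0.0824 + 0.2471 + 0.3177 = 0.6471 (unrounded terms)

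The products are 0.9743² = 0.949, 0.9743 × 0.6471 = 0.630 and 0.6471² = 0.419.

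At limit 0 they are 0.4783² = 0.229, 0.4783 × 0.0824 = 0.039 and 0.0824² = 0.007.

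**Step 3. Separate out ties.** P(tie) = Σ P(X = x) P(Y = x). Ties at 2 or fewer responses are already inside the limit-2 figures of Step 2, so they are shown apart.

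| Quantity | 0.1 / 0.1 | 0.3 / 0.1 | 0.3 / 0.3 |
|---|---|---|---|
| Both ≤ 2 | 0.949 | 0.630 | 0.419 |
| of which tied | 0.383 | 0.171 | 0.169 |
| of which not tied | 0.567 | 0.460 | 0.250 |
| Tied, both ≥ 3 | 0.0005 | 0.005 | 0.062 |
| Both 0 of 7 (all ties) | 0.229 | 0.039 | 0.007 |
| Tied, both ≥ 1 | 0.154 | 0.137 | 0.224 |

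The last row is all ties less 0-0 ties: 0.3831 − 0.2288 = 0.154, 0.1762 − 0.0394 = 0.137 and 0.2303 − 0.0068 = 0.224.

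The untied row is the clearest conflict: one identifiable leading arm that Section 6.1 expands and Section 14.0 stops. In a tie at or below the limit, Section 6.1 identifies no arm but still gives a total of 25, so the disagreement over whether to continue remains.

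**The case against.** The strongest reply is that Section 6.1 only summarizes and Section 14.0 operates. Section 14.0 also gives a total of 25 next to toxicity rules that can end the trial earlier, and Section 3.2 says the figure is approximate, so 25 can be read as a planned maximum. The winning arm in Section 14.0 can be read as the better of the arms not stopped. This is a fair reading and may be what was intended. But Section 6.1, which directs enrollment, carries no such condition and does not refer to the Section 14.0 limit. The reading also leaves ties unanswered.

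Three stronger readings are tempting, and the documents do not support them.

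- **That the sections conflict in 42% to 95% of trials.** Those ends hold only for independent arms with both true rates at 0.3 or both at 0.1, and only at the limit of 2. At rates of 0.4 and 0.3 the figure is 27%; at 0.5 and 0.5 it is 5%. At a limit of 0 the range is 0.7% to 23%, and every such case is a 0-0 tie, so no leading arm is both stopped and expanded.
- **That the missing stop in Section 6.1 drives the error rates.** With ties broken at random, the chance of at least 4 of 18 in the expanded arm is 0.153 (both rates 0.1) and 0.922 (both 0.3) under Section 6.1, against 0.037 and 0.574 under Section 14.0 as written. At a limit of 0, Section 14.0 gives 0.149 and 0.920. Nearly all of the contrast belongs to the limit.
- **That this is the trial's only adaptive decision.** Section 14.0 also has Bayesian toxicity stopping from the third patient.

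**Conclusion.** The point holds as an inconsistency in the current text with two parts: opposite instructions when both arms are at or below the stage-1 limit, and no rule for a tie.

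Under independence and the limit as written, the first part arises with probability 0.949, 0.630 or 0.419 at true rates 0.1/0.1, 0.3/0.1 and 0.3/0.3, or 0.567, 0.460 and 0.250 without ties. Most of this size comes from the limit of 2, which does not fit the stated type I error and power. At 0 of 7 the figures fall to 0.229, 0.039 and 0.007.

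The tie gap moves the other way. Ties with both arms above the limit occur in 0.05%, 0.5% and 6.2% of trials at a limit of 2, but in 15.4%, 13.7% and 22.4% at a limit of 0. Correcting the limit therefore shrinks the first part and makes the tie rule more important.

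**What to change.** Amend Section 6.1 and Section 14.0 together.

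- Reconcile the stage-1 limit in Section 14.0 with its stated type I error and power. Aligning Section 6.1 to the limit of 2 alone would leave the chance of at least 4 of 18 in the expanded arm at only 0.574 (rates 0.3/0.3) or 0.360 (0.3/0.1), with ties broken at random.
- State in Section 6.1 that the arm with more responses enrolls 11 more patients only if it exceeds the Section 14.0 limit, and that enrollment ends at 14 if neither arm does.
- State that if both arms exceed the limit with equal counts, the expanded arm is set by a rule fixed before the interim: a named stratum, or a random draw by the statistician.
- Describe 25 as the maximum enrollment wherever it appears (Protocol Summary, Sections 3.2, 6.1 and 14.0), with a stop at 14 for too few responses and an earlier toxicity stop both possible.

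The cost is protocol wording in a few places and no additional patients. The text should be settled before interim responses are seen.

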	
was subsequently validated in an independent cohort of 223 MDS patients derived from the Groupe Francophone des Myélodysplasies (GFM) database and in a phase III randomized clinical trial. Thus, risk stratifying MDS patients by the new model at the time of HMA failure may open new opportunity for drug approvals in this setting⁵⁻⁶.
 
Identifying novel drugs that can improve the outcome of MDS patients after HMA failure remains an unmet need.

Primary Objective	
Evaluate the efficacy of CPX-351 as measured by overall response rate (ORR), i.e. by IWG 2006 criteria for MDS patients after Hypomethylating agent failure.
 
Endpoint and time frame: Overall response rate (ORR), i.e. by IWG 2006 criteria for MDS and patients at end of induction (C1D35 +/-10).

Secondary Objective(s)	
 • To determine the time to response (TTR) associated with CPX-351 in patients with MDS 
Endpoint and time frame: TTR associated with CPX-351 in patient with MDS at the end of induction (C1D35 +/-10).
 
 • To evaluate the duration of response (DOR) in patients achieving a response 
Endpoint and time frame: DOR in patients achieving a response at the time of response (C1D35 +/-10) and up to 1 year after the end of treatment.
 
 • To evaluate the event-free survival (EFS) and the overall survival (OS) probability of all patients enrolled in this trial. 
Endpoint and time frame: EFS and OS probability of all patients enrolled in this trial at end of induction (C1D35 +/-10) and up to 1 year after the end of treatment.

Estimated Study Duration	
Estimated date first subject enrolled: March, 2019
 
Estimated date last subject enrolled: March, 2020

Duration of Participation	Patient participation is expected to average 6 to 12 months
Sample Size	25 patients

Disease sites/Conditions	Myelodysplastic Syndrome (MDS)
Interventions	
 • CPX-351 44mg/m² (daunorubicin 44 mg/m² and cytarabine 100 mg/m²), IV days 1, 3, and 5 during the induction phase. • CPX-351 15.4mg/m² (daunorubicin 15.4 mg/m² and cytarabine 35 mg/m²), IV every 28 days for up to 4 cycles during the consolidation phase for patients achieving a response.

Abbreviations

AE	Adverse Event
ALL	Acute Lymphoblastic Leukemia
ALT	Alanine Aminotransferase
AML	Acute Myeloid Leukemia
AML-MRC	Acute Myeloid Leukemia with Myelodysplasia Related Changes

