3.0 Study Design

3.1 Overview of Study Design

This is a phase II study of single agent CPX-351 administered at the standard FDA approved dose of 44 mg/m² (daunorubicin 44 mg/m² and cytarabine 100 mg/m²) intravenously on days 1, 3, 5 of the induction cycle. If patients achieve complete remission (CR), complete remission with incomplete count recovery (CRi) or partial remission (PR) (section 12.0, Table 2) they will be eligible to continue on to consolidation therapy, which will consist of CPX-351 at a dose of 15.4 mg/m² (daunorubicin 15.4 mg/m² and cytarabine 35 mg/m²) every 28 days. Patients can receive up to 4 cycles of consolidation therapy.

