3.4 Expected Duration of Treatment and Subject Participation

Enrollment to this study is estimated to occur over three years. Upon signing consent, patients will undergo screening to determine if the patient meets all inclusion and exclusion criteria, as outlined in section 4.1 and 4.2. Following screening, all eligible patients will be enrolled and begin induction therapy which will occur over a 35 day cycle and/or at count recovery with CPX-351 dosing on days 1, 3 and 5.

Patients who achieve a response (section 12.0, Table 2) may proceed with the consolidation phase of the trial with CPX-351 dosing on days 1 and 3 of every 28 days. Patients can receive up to 4 cycles of consolidation. Treatment will continue during the duration of the study unless patients exhibit evidence of treatment failure, disease progression, experience an unacceptable toxicity, or the investigator determines that discontinuation of treatment is in the best interest of the patient. Patients will be treated with CPX-351 based on a calculation determined from the patient's body surface area (BSA). BSA will be calculated before each day of dosing and will be based on the patient's height (measured at baseline) and weight (measured each visit).

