The consolidation phase is defined as C2D1 to C5D28 or once the patients meet EOT criteria (section 6.3, Table 1). Only patients with a documented response (CR, CRI, or PR) from the D35 (+/-10 days) bone marrow are eligible for consolidation therapy. Prior to the first cycle of consolidation therapy the patients must have a PS of 0-2. During the consolidation phase, CPX-351 must be given no earlier than 35 days after the start of induction and no later than 75 days after the start of induction. For all subsequent cycles, there must be at least 35 days between the start of each cycle. Patients must have recovered to ANC >500/ µL and platelets >50,000/µL to be eligible for any consolidation therapy.

During the consolidation phase, CPX-351 will be given at 15.4 mg/m² (daunorubicin 15.4 mg/m² and cytarabine 35 mg/m²) on days 1 and 3 of each 28 day cycle. Consolidation therapy can be continued up to 4 cycles in the absences of toxicities or reasons that require discontinuation and/or any EOT criteria (section 6.3, Table 1).

Premedication with anti-emetics is recommended prior to treatment with CPX-351. No other chemotherapy consolidation treatment is permitted. Only HSCT (hematopoietic stem cell transplant) is permitted in place of, or following, chemotherapy consolidation. Delays in administrating consolidation cycles will be allowed at the discretion of the treating physician and after discussion with the PI.

End of Treatment and Follow-up

At the point in which the patient completes therapy per protocol or meets any EOT criteria (section 6.3, Table 1), the patient will enter into the follow-up period. The patient will be followed for survival for 1 year and/or until death, whichever occurs first. During the first 6 months of follow-up the patient will be seen in clinic as standard of care (SOC) every 30 days, per the study calendar (section 11.2). End of study (EOS) is defined as the time the patient completes 1 year of follow, withdraws consent and/or patient's death, whichever occurs first.

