12. Documentation in the medical record (consisting of start and stop date, dose, frequency and route) of any prior administration of cancer agent therapy.
13. Documentation in the medical record of all adverse events (graded per CTCAE V. 5.0). Documentation must include start and stop dates (if resolved), relationship to CPX-351 and grade.

Consolidation Therapy (C2D1 to C5D28)

1. Physical examination on day 1 of each 28 day cycle (Appendix IV).
2. ECOG performance status will be collected on day 1 of each 28 day cycle (Appendix I).
3. Vitals will be collected prior to dosing on days 1 and 3 (Appendix IV).
4. Echocardiogram will be completed prior to dosing on day 1 of every cycle
5. Hematology exam on dosing days 1 and 3 of and twice weekly during each 28 day cycle (Appendix IV).
6. Serum chemistry exam on dosing days 1 and 3 and twice weekly during each 28 day cycle (Appendix IV).
7. Administration of CPX-351 at 15.4mg/m² (daunorubicin 15.4 mg/m² and cytarabine 35 mg/m²) on days 1 and 3 of every 28 day cycle
8. Serum pregnancy test will be collected on day 1 of every 28 day cycle, only for women of childbearing potential. Child bearing potential is defined as not post-menopausal for 12 months or no previous surgical sterilization.

9. Documentation in the medical record (consisting of start date, dose, frequency, route, and if applicable stop date) of all medications including vitamins and other over the counter medications will be collected on day one of every 28 day cycle.
10. Documentation in the medical record (consisting of start and stop date, dose, frequency and route) of any prior administration of cancer agent therapy will be collected on day one of every 28 day cycle.
11. Documentation in the medical record of all adverse events (graded per CTCAE V. 5.0). Documentation must include start and stop dates (if resolved), relationship to CPX-351 and grade will be collected on day one of every 28 day cycle.

End of Treatment (EOT)

1. Physical examination (Appendix IV).
2. ECOG performance status (Appendix I).
3. Vitals (Appendix IV).
4. Hematology exam (Appendix IV).
5. Serum chemistry exam (Appendix IV).
6. Bone marrow aspirate and biopsy, including cytogenetics.
7. Disease assessment (Table 2).
8. Documentation in the medical record (consisting of start date, dose, frequency, route, and if applicable stop date) of all medications including vitamins and other over the counter medications will be collected.

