11.2 Calendar

Period	Screening Period	Induction Phase							Consolidation Phase				End of Treatment (EOT)	Follow-up ^g
		1 cycle							Up to 4 cycles					
Day	28 Days	1	2	3	4	5	6-27	35 ^l	1 ^{dij}	2	3	4 - 28		
CPX-351 Administration ^a		X		X		X			X		X			
Informed Consent Form (ICF)		X												
Disease history and prior therapies		X												
History and physical exam ^b		X							X				X	
Vital signs ^b		X	X ^{op}		X ^{op}				X	X ^{op}		X ^{op}		
Concomitant medications		X	X							X			X	
ECOG performance status ^c		X								X			X	
Hematology ^b		X	X	X	X	X	X	X ⁿ	X	X ^e		X ⁿ	X	X ^g
Serum chemistry ^b		X	X	X	X	X	X	X ⁿ	X	X ^e		X ⁿ	X	
Pregnancy test		X	X ^k							X ^k				
Echocardiogram		X ^r	X ^q							X				
Electrocardiogram		X ^r												
Bone marrow biopsy and aspiration ^b		X ^r							X				X	
Disease response assessment ^f		X							X				X	
Correlative analysis blood draw ^m		X							X				X	
Survival follow-up														X ^h
Adverse event assessment									← X →					

- a: During the induction phase all patients will receive 44mg/m². Following the induction phase if patients achieve a response (per section 12.0) they may continue onto the consolidation phase. During the consolidation phase patients will receive 15.4mg/m² (daunorubicin 15.4 mg/m² and cytarabine 35 mg/m²) for up to 4 cycles.
- b: See Appendix IV for required tests.
- c: See Appendix I for performance status grading.
- d: Indicates at +/-3 day window.
- e: Required twice weekly to monitor counts, can be completed at a local laboratory.
- f: See Section 12.0 for MDS response assessment criteria.
- g: Follow up will occur monthly as SOC for the first 6 months of follow-up. See section 6.4 for adverse event reporting requirements.
- h: Survival Follow up will occur bimonthly (60 days) for a duration of 1 year from patient's EOT visit.
- i: During only the first cycle in consolidation phase, CPX-351 must be given no earlier than 35 days after the start of induction and no later than 75 days after the start of induction. There should be 35 days between the start of each subsequent consolidation cycles. Patients must have recovered to ANC >500/ μ L and platelets >50,000/ μ L to be eligible for any consolidation therapy.
- j: Prior to the first cycle of consolidation therapy, patient must have an ECOG PS of 0-2.
- k: Must be negative prior to dosing.
- l: Indicates a +/-10 day window.
- m: 10mL of whole blood will be collected in an extra lab tube for these tests.

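### Consolidation is dosed every 28 days in the Summary, 3.1 and 3.4, but Section 6.1 requires at least 35 days between the starts of subsequent cycles

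*Combined protocol and SAP*

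**What the plan says.** Two intervals appear in current operative text.

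**35 days**
- Section 6.1, Consolidation: "For all subsequent cycles, there must be at least 35 days between the start of each cycle".
- Section 11.2, calendar footnote i, attached to consolidation Day 1: "There should be 35 days between the start of each subsequent consolidation cycles". This is weaker than 6.1, with neither a mandatory verb nor a stated minimum.

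**28 days as a dosing frequency**
- Protocol Summary, Interventions: "IV every 28 days for up to 4 cycles during the consolidation phase for patients achieving a response".
- Section 3.1: "every 28 days. Patients can receive up to 4 cycles of consolidation therapy".
- Section 3.4: "CPX-351 dosing on days 1 and 3 of every 28 days".

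**28 days as a cycle length**
- Section 6.1, in the paragraph after the 35-day rule: "on days 1 and 3 of each 28 day cycle".
- Section 11.1, Consolidation Therapy: "on days 1 and 3 of every 28 day cycle".

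Related provisions:
- The first consolidation cycle must start 35 to 75 days after the start of induction (6.1 and footnote i).
- Every consolidation cycle requires ANC above 500/µL and platelets above 50,000/µL.
- Consolidation Day 1 carries a ±3 day window (footnote d).
- Delays are at the physician's discretion after discussion with the PI (6.1).
- No dose reductions are allowed (7.0).

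**The concern.** A site cannot follow both intervals. If it works from the Summary, 3.1 or 3.4, it plans the next cycle 28 days after the last and departs from a mandatory rule in the treatment section. If it works from 6.1, it departs from the frequency stated in three other places.

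The drug is myelosuppressive. Section 1.2.2 itself reports slower neutrophil and platelet recovery with CPX-351 than with 7+3 in the phase 3 AML study. With dose reductions ruled out, the spacing of cycles is one of the few remaining controls on exposure. Patients could therefore receive different dose intensity depending on which section their site reads, and a correct cycle under one section would be a deviation under another. Follow-up runs for one year from end of treatment, so the interval also moves the end of follow-up for patients who complete consolidation.

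**Working it through.** The plan gives no derived figure to reproduce. The check is a comparison of the statements plus day and dose arithmetic.

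**Inputs**
- Interval: 28 days (Summary, 3.1, 3.4) or at least 35 days (6.1).
- Up to 4 consolidation cycles, hence 3 intervals between starts.
- Dose: daunorubicin 15.4 mg/m² and cytarabine 35 mg/m² on each of Days 1 and 3 (3.4, 6.1, 11.1, calendar).
- Window on Day 1: ±3 days (footnote d).

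**Step 1: shortfall for a cycle on the 28-day schedule.** 35 − 28 = 7 days.

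**Step 2: can the visit window bridge it?** Footnote d does not say whether the window counts from the actual previous start or from planned dates.

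| Anchor | Shortest interval | Longest interval |
|---|---|---|
| Actual previous start | 28 − 3 = 25 | 28 + 3 = 31 |
| Planned dates, both cycles moved | 28 − 3 − 3 = 22 | 28 + 3 + 3 = 34 |

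The longest possible interval, 34 days, is still under 35.

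**Step 3: length of consolidation.**
- C2D1 to C5D1: 3 × 28 = 84 days, versus at least 3 × 35 = 105 days. Difference: at least 21 days.
- Earliest C5D1 after the start of induction, with C2D1 at 35 days: 35 + 84 = 119 versus 35 + 105 = 140 days.

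**Step 4: planned dose intensity.**
- Daunorubicin per cycle: 2 × 15.4 = 30.8 mg/m². Over 4 weeks, 30.8 / 4 = 7.70 mg/m² per week; over 5 weeks, 30.8 / 5 = 6.16. Ratio 6.16 / 7.70 = 0.80.
- Cytarabine per cycle: 2 × 35 = 70 mg/m². 70 / 4 = 17.5 versus 70 / 5 = 14.0 mg/m² per week, the same 20% reduction.

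The 35-day figures are upper limits, because 35 days is a minimum interval.

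**Step 5: who is affected.** The start of the first consolidation cycle has its own 35 to 75 day window, which no other statement contradicts. The conflict begins with the second consolidation cycle.

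**The case against.** The strongest defence is that 28 days is the length of a cycle and 35 days is the spacing of starts, with a rest week between. That would reconcile the cycle-length wording in 6.1 and 11.1. It does not reconcile the Summary, 3.1 and 3.4, which state how often the drug is given, and nothing in the protocol describes a rest week.

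A second defence is that delays are allowed. The clause permits a later start at the physician's discretion; it does not make a 28-day start compliant with a mandatory minimum.

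A third is that the count requirement protects patients. This largely stands. It applies to every consolidation cycle and limits the harm. A reader might infer that patients would be re-dosed before marrow recovery; the documents do not support that. What remains is that a patient who has recovered by day 28 may be dosed under 3.4 but not under 6.1.

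A reader might also infer a monitoring hole in days 29 to 35, because Section 11.1 reads "Hematology exam on dosing days 1 and 3 of and twice weekly during each 28 day cycle" and the calendar column ends at Day 28. That would overstate it. Footnote n, which marks the later consolidation days in the calendar, allows counts one to three times weekly at the physician's discretion, and the recovery requirement implies counts before the next Day 1. The schedule for that week is unnamed, which is a minor matter.

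Appendix II, which runs consolidation from C2D1 through C5D28, fits either interval and settles nothing. The dosing days do not conflict: the Summary and 3.1 simply omit Days 1 and 3.

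**Conclusion.** The contradiction is real and should be fixed. A 28-day schedule is 7 days short of the 6.1 minimum, and neither the visit window, the delay clause nor the count requirement removes the conflict. For a patient given all four cycles, the two readings differ by at least 21 days from first to last cycle start and by 20% in planned weekly dose. These figures assume two doses per cycle and starts exactly at the stated interval.

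The scope is narrow: only responders who receive two or more consolidation cycles. Transplant in place of consolidation, relapse, toxicity or failure of count recovery would each reduce that group further. A reader might infer that a dosing contradiction weakens the trial's main result. It does not: response is assessed at the end of induction (C1D35 ±10 days), before consolidation begins, and no sample-size figure depends on the consolidation interval.

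**What to change.** The sponsor should first confirm that the explicit 35-day rule in 6.1 governs. Then:

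- In the Summary, 3.1 and 3.4, replace the 28-day frequency with: Days 1 and 3, with at least 35 days between cycle starts.
- In 6.1 and 11.1, state that the 28-day cycle is followed by at least 7 further days before the next start.
- In footnote i, make the 35 days a mandatory minimum, as in 6.1.
- State that the −3 side of the visit window may not shorten the 35 days.
- In 11.1 and 11.2, say whether counts continue from day 29 to the next Day 1.

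Appendix II and the C5D28 label can stay. If the sponsor instead intends 28 days, 6.1 and footnote i are the places to change.

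The cost is a wording amendment. Sites now dosing every 28 days would take at least 21 more days to give four cycles. If counts are continued through days 29 to 35, the three gaps add 3 × 1 = 3 to 3 × 3 = 9 draws per patient completing four cycles under footnote n, or 3 × 2 = 6 at the twice-weekly rate in 11.1. These can be done at a local laboratory.
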